8.4.5.1 Analysis for Secondary Pharmacodynamic Endpoints

The secondary PD variable is the difference in the mean change from baseline to the end of the impatient period (i.e. day 7) in the average glucose based on 7-point central laboratory glucose monitoring. Summary statistics will be provided for each study arm. Also, the difference between each dapagliflozin (1 mg, 2.5 mg, 5 mg and 10 mg per day) plus insulin versus placebo plus insulin will be summarized. The existence of a dose related trend pattern will be assessed.

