8 STATISTICAL CONSIDERATIONS

8.1 Sample Size Determination

Given that this study is designed for exploratory analysis, formal statistical hypothesis testing is not planned. Therefore, the sample size for this study is not based on any formal

power considerations. The sample size target is approximately 14 subjects per study arm, i.e. a total of approximately 70 subjects to be randomized to dapagliflozin 1, 2.5, 5, 10 mg and placebo in 1:1:1:1:1 ratio. Although the number of subjects is not based on statistical power considerations, 14 subjects per treatment group will provide 80% probability of observing at least one occurrence of any adverse event in a group assuming the incidence rate is 11 per hundred subjects in 14 days.

Analysis will include the estimation of frequencies (for categorical endpoints) or summary statistics such as mean and 95% confidence intervals (for continuous endpoints) for each treatment arm.

The primary objective of the study is to assess the safety and tolerability of each dose of dapagliflozin (1 mg, 2.5 mg, 5 mg and 10 mg per day) plus insulin after 14 days of oral administration of double-blind treatment. The number of subjects that experience events of major, minor and other hypoglycemia, serious adverse events, deaths, adverse events leading to discontinuation of study therapy, adverse events of interest of genitourinary infection and potentially clinically significant changes in vital signs during the 14 days of dapagliflozin exposure will be summarized by treatment group. All adverse events that are serious or that result in discontinuation of study therapy will be described in depth. No sample size determination or estimates of variations of incidence or summary statistics is calculated for safety and tolerability endpoints.

A secondary objective of the study is to assess the pharmacokinetics of dapagliflozin and its major inactive metabolite, dapagliflozin 3-O-gulcuronide, on Day 7. No sample size determination or estimates of variation are calculated for this objective, either.

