An additional secondary endpoint, related to pharmacodynamics, is the change from baseline to Day 7 in mean glucose based on 7-point central laboratory glucose monitoring, which will be summarized for each study arm. Also, the difference between each dapagliflozin dose (1 mg, 2.5 mg, 5 mg and 10 mg per day) plus insulin versus placebo plus insulin will be summarized. Assuming a common standard deviation of 30 mg/dL in each treatment group, with 14 subjects per group, the half-width of the 95% confidence interval for the difference between any dapagliflozin + insulin treatment group and the placebo + insulin treatment group is estimated to be 22.22 mg/dL.

8.2 **Populations for Analyses**

- The pharmacodynamic dataset is the Randomized Subjects dataset which is defined as all randomized subjects who receive at least one dose of double-blind study medication. Whenever using the Randomized Subjects dataset, subjects will be presented in the treatment group to which they were randomized at the start of the double-blind treatment period (even if the treatment they received was different). In addition, randomized subjects must have both a baseline and at least one post-baseline measurement for the time point under consideration to be included in the pharmacodynamic analysis of change or percent change from baseline. All efficacy analyses will be performed using the pharmacodynamic dataset.
- The safety data set is the Treated Subjects dataset which is defined as all treated subjects who received at least one dose of study medication. The Treated Subjects Data Set consists of all subjects who received at least one dose of double-blind study medication during the double-blind treatment period. The Treated Subjects Data Set would include any subject who accidentally received double-blind study medication but was not randomized in the study. All analyses using the Treated Subject Data Set will be presented by randomized treatment group, except in cases where information was available which indicated that a subject received a different treatment for the entire course of their participation in the study (or period).In this case, the safety data for those subjects will be presented by the treatment actually received. In case a subject never received the treatment as assigned by randomization, then the safety data for that subject will be presented by the first treatment received. All safety analyses will be performed using the safety data set.

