- Pharmacokinetics data set consists of all available concentration-time data from subjects who receive dapagliflozin. All available derived pharmacokinetics parameter values will be included in the pharmacokinetics data set and reported. All pharmacokinetic analyses will be performed using the pharmacokinetics data set, but only subjects with adequate PK profiles will be included in the summary statistics and statistical analysis.

Randomization will be stratified by body mass index (BMI) categorization ($\leq 23 \text{ kg/m}^2$ vs. > 23 kg/m²) and method of insulin administration (pump or daily injections) to ensure equal representation across all treatment groups.

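### The 22.22 mg/dL half-width in 8.1 is a known-SD value, 2–5% too favourable for a t interval, and baseline and stratum adjustment would serve the comparison better

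*Protocol*

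**What the plan says.** Section 8.1 (Sample Size Determination) says that the study is exploratory, that no formal testing is planned and that the sample size does not rest on power. For the secondary pharmacodynamic endpoint it then gives one precision figure. The inputs are "Assuming a common standard deviation of 30 mg/dL in each treatment group" and "with 14 subjects per group". The result concerns "the half-width of the 95% confidence interval for the difference between any dapagliflozin + insulin treatment group and the placebo + insulin treatment group", for which the section gives 22.22 mg/dL. Allocation is to active doses and "placebo in 1:1:1:1:1 ratio".

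Section 8.4.5.1 defines the comparison: "The secondary PD variable is the difference in the mean change from baseline to the end of the impatient period (i.e. day 7"), based on 7-point central laboratory glucose. It promises summary statistics per arm, a summary of each dose's difference from placebo, and an assessment of dose trend. It names no estimator, model or covariate.

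Section 8.2 repeats that randomization is stratified by BMI (at or below 23 kg/m² versus above) and by "method of insulin administration (pump or daily injections) to ensure equal representation across all treatment groups". No analysis section says whether these factors enter the analysis. Table 5.1.1 schedules 7-point glucose on Day -1, Day 1 and Day 7, so a full pre-treatment profile is available. ANCOVA appears in the abbreviation list (section 11) and nowhere else.

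**The concern.** The half-width is the only confidence interval precision stated for this trial. A figure of 22.22 matches a normal multiplier applied to an assumed SD. The reported interval will use an SD estimated from small arms, and that calls for a t multiplier and a wider interval.

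The description in 8.4.5.1, read beside a planning formula with no covariates, is that of a plain contrast of change scores. With 14 per arm, chance imbalance in baseline glucose is likely, and a change score does not fully remove its effect. Adjusting for a baseline that is already measured, and for the factors used to stratify, costs very little. At stake is how precisely the dose-versus-placebo differences are estimated in a study meant to inform dose selection for later type 1 diabetes trials (section 1.1).

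**Working it through.** **Inputs.** From section 8.1: SD 30 mg/dL, n = 14 per arm, five equal arms (70 subjects), 95% confidence. The protocol does not say whether 30 is the SD of the change or of a single day's mean. The change is the natural reading, because the endpoint is a change. The correlation ρ between baseline and Day 7 is not given and is an assumption below.

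**1. The stated figure.**
- Standard error of a difference: 30 × √(2/14) = 11.339.
- Normal multiplier: 1.95996 × 11.339 = 22.22 mg/dL. This reproduces section 8.1: known SD, two-sample, no covariates, no losses.

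**2. The same inputs with the SD estimated.**

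| SD estimated from | df | t(0.975) | Half-width (mg/dL) | Excess over 22.22 |
|---|---|---|---|---|
| five arms pooled | 70 − 5 = 65 | 1.9971 | 22.65 | 0.42 (1.9%) |
| the two arms compared | 28 − 2 = 26 | 2.0555 | 23.31 | 1.09 (4.9%) |

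Taken the other way, an interval of ±22.22 at this standard error covers 94.6% (65 df) or 93.9% (26 df). A t half-width no greater than 22.22 needs 15 per arm with pooling (21.85), or 16 per arm with two arms (21.66; 15 gives 22.44).

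**3. What baseline adjustment would do.** Let the variance be σ² at both times.
- Variance of the change: 2σ²(1 − ρ).
- Residual variance after adjusting for baseline: σ²(1 − ρ²).
- Ratio: (1 + ρ)/2.
- Residual df with baseline and two binary factors: 65 − 3 = 62, t = 1.9990. With the same SD of 30 the half-width would be 1.9990 × 11.339 = 22.67, so the three df add only about 0.02 mg/dL to 22.65.
- Adjusted half-width, if 30 is the SD of the change: 22.67 × √((1 + ρ)/2).

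| Assumed ρ | √((1 + ρ)/2) | Half-width (mg/dL) |
|---|---|---|
| 0.3 | 0.806 | 18.3 |
| 0.5 | 0.866 | 19.6 |
| 0.7 | 0.922 | 20.9 |
| 0.8 | 0.949 | 21.5 |

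These figures take no credit for the strata and leave out the small loss from chance baseline imbalance. The adjusted half-width falls below 22.22 when (1 + ρ)/2 < (22.22/22.67)² ≈ 0.961, that is, for ρ below about 0.92.

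**The case against.** **The gap is trivial for a planning figure.** Section 8.1 calls the value an estimate and conditions it on an assumed SD, for which a normal quantile is an ordinary approximation. Changing the assumed SD from 30 to 31 moves the half-width by 1.96 × 1 × √(2/14) = 0.74 mg/dL, more than the pooled-t correction of 0.42. No sample size, test or decision depends on it, and the final interval will use the observed SD. All of this stands and limits the weight of the point. The figure is still easily put right.

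**The protocol does not commit to an unadjusted analysis.** A reader might infer from 8.4.5.1 that baseline and the strata are to be ignored. The text does not support that. It names the quantity, a difference in mean change, and ANCOVA of the change estimates the same quantity. A formula without covariates in 8.1 does not fix the analysis, the abbreviation list includes ANCOVA, and a protocol commonly leaves covariates to a statistical analysis plan, which is not at hand here. Silence on covariates is therefore not an error. What remains is a recommendation to name a better estimator than the one described.

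**A reader might also infer that an interval without the strata must be too wide.** That holds only if BMI or insulin method predicts the glucose change, and the protocol gives no evidence either way.

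**The two halves may seem to pull apart.** The figure of 22.22 is too small for an unadjusted t interval, but may be too large for an adjusted one. Both statements are true, because they concern different estimators. This is why the figure in 8.1 needs a label saying which analysis it describes.

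**Conclusion.** The point holds in a limited form. As the half-width of an unadjusted 95% interval with estimated SD, 22.22 mg/dL is too favourable by 0.42 mg/dL (1.9%, pooled over five arms) to 1.09 mg/dL (4.9%, two arms). This rests only on the protocol's own SD of 30 and 14 per arm, with every subject evaluable.

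The gain from adjustment is less certain. The range of 18.3 to 21.5 mg/dL requires that 30 is the SD of the change, that variances are equal at baseline and Day 7, and that the correlation lies between 0.3 and 0.8. None of these is stated. The gain shrinks as the correlation rises.

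The documents do not show that baseline and strata will be left out, or that the final interval will be wider than 22.22. They give no dropout figure from which to size a loss, and section 8.4.5 carries the last inpatient value forward. The point is also confined to the 7-point glucose comparison: for the other pharmacodynamic endpoints, 8.4.5.2 specifies intervals within each arm.

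**What to change.** - **Section 8.1:** replace 22.22 mg/dL by 22.65 mg/dL if the SD is pooled over five arms, or 23.31 mg/dL if only the two arms compared are used. Label it as t-based, unadjusted and without losses, and say whether 30 mg/dL is the SD of the change.
- **Section 8.4.5.1:** state that differences from placebo are estimated by ANCOVA of the change in 7-point mean glucose on treatment arm, Day -1 7-point mean glucose, BMI stratum and insulin-method stratum, with t-based 95% confidence intervals. If a statistical analysis plan already says this, a cross-reference is enough.

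The cost is a few sentences and 3 degrees of freedom (65 to 62). The stated precision becomes slightly less favourable. Data collection, sample size and study conduct do not change.

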8.4.5.2 Analysis for Other Pharmacodynamic Endpoints

Other continuous variables listed below will be summarized at each time point of assessment. A point estimates and 95% confidence intervals for the mean change (percent change) from baseline will be provided within each treatment group. No p-values will be generated.

Change from baseline will be summarized for:

- a) Fasting Plasma Glucose (FPG)
- b) 24-hr urinary glucose
- c) percent inhibition of renal glucose reabsorption
- d) Systolic blood pressure (SBP)

Percent change from baseline will be summarized for:

a) 7 days of double-blind treatment in total daily insulin dose.

The percent of 24-hour glucose readings obtained from continuous glucose monitoring system (CGMS) that fall within the ranges: $\leq 50 \text{ mg/dL}$, $\leq 70 \text{ mg/dL}$, 71 - 180 mg/dL and > 180 mg/dL will also be summarized.

The variability of glucose measurements from CGMS will also be assessed

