1.3 Objectives

Primary Objective:

To assess the safety and tolerability of each dose of dapagliflozin (1 mg, 2.5 mg, 5 mg and 10 mg per day) plus insulin after up to 14 days of oral administration of double-blind treatment, as measured by numbers of subjects with SAEs, deaths or discontinuations due to AEs, events of hypoglycemia, AEs of genitourinary infection, or potentially clinically significant changes in vital signs.

Secondary Objectives:

- 1) To assess the change from baseline in mean glucose based on 7-point central laboratory glucose monitoring achieved with dapagliflozin (1 mg, 2.5 mg, 5 mg and 10 mg per day) plus insulin versus placebo plus insulin after 7 days of oral administration of double-blind treatment.
- 2) To assess the pharmacokinetics of dapagliflozin and its major inactive metabolite, dapagliflozin 3-O-glucuronide, on Day 7.

Other/Exploratory Objectives:

- 1) To assess the change from baseline (Day -1) in the percent of 24-hour glucose readings obtained from continuous glucose monitoring system (CGMS) during the inpatient stay after 7 days of double-blind treatment with dapagliflozin plus insulin versus placebo plus insulin that fall within the following ranges:
 - a) $\leq 50 \text{ mg/dL}$
 - b) $\leq 70 \text{ mg/dL}$
 - c) 71 180 mg/dL
 - d) > 180 mg/dL
- 2) To assess change from baseline (Day -1) in glucose variability estimated from CGMS with dapagliflozin plus insulin versus placebo plus insulin after 7 days of oral administration of double-blind treatment

dapagliflozin	MB102072
BMS-512148	Clinical Protocol

- 3) To assess the percent change from baseline (Day -1) during the inpatient stay in total daily insulin dose with dapagliflozin plus insulin versus placebo plus insulin after 7 days of oral administration of double-blind treatment
- 4) To assess the change from baseline achieved with dapagliflozin (1 mg, 2.5 mg, 5 mg and 10 mg per day) plus insulin versus placebo plus insulin after 7 days of oral administration of double-blind treatment, for Fasting Plasma Glucose (FPG)
- 5) To assess the effect of dapagliflozin dose on 24 h urinary glucose excretion and the percent inhibition of renal glucose reabsorption after 7 days of oral administration of double-blind treatment.

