- 6) To assess the change from baseline in systolic blood pressure (SBP) achieved with dapagliflozin (1 mg, 2.5 mg, 5 mg and 10 mg per day) plus insulin versus placebo plus insulin after 7 and 14 days of oral administration of double-blind treatment.
- 7) To assess other safety and tolerability parameters including: proportion of subjects with adverse events (not included in the primary objective) and marked abnormalities in clinical laboratory tests, as well as the change from baseline at each post-baseline time point of selected safety clinical laboratory parameters, physical measurements, vital signs and electrocardiogram data after 14 days of oral administration of double-blind treatment.

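### Five exploratory objectives ask for a comparison with placebo, but section 8.4.5.2 plans intervals only within each arm (FPG, SBP, insulin dose) or names no contrast (CGMS measures)

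*Protocol*

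**What the plan says.** Section 1.3 sets five of the seven exploratory objectives as comparisons with the placebo arm:

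- Objective 1, CGMS ranges: "double-blind treatment with dapagliflozin plus insulin versus placebo plus insulin that fall within the following ranges".
- Objective 2, CGMS variability: "To assess change from baseline (Day -1) in glucose variability estimated from CGMS with dapagliflozin plus insulin versus placebo plus insulin".
- Objectives 3 and 4, percent change in total daily insulin dose and change in fasting plasma glucose (FPG), carry the same comparator.
- Objective 6, systolic blood pressure (SBP): "plus insulin versus placebo plus insulin after 7 and 14 days of oral administration of double-blind treatment".

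Objective 5 (urinary glucose and inhibition of renal glucose reabsorption) and objective 7 (other safety measures) name no placebo comparison.

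Section 8.4.5.2 gives the analysis of these endpoints: "A point estimates and 95% confidence intervals for the mean change (percent change) from baseline will be provided within each treatment group". The list that follows includes FPG, SBP and total daily insulin dose, and p-values are ruled out. For the CGMS ranges the section says only that they will be summarized, and for CGMS variability only that it will be assessed.

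Section 8.4.5.1 treats the secondary endpoint, 7-point mean glucose, differently. Beside the per-arm summaries it plans a summary of the difference between each dose and placebo. Section 8.1 gives the precision of that difference.

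**The concern.** An interval for the mean change within one arm describes how far that arm moved from its baseline. It does not give the difference from placebo or the uncertainty of that difference, which is what objectives 1 to 4 and 6 ask for.

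The distinction matters because the arms share influences that can move these measurements without any drug effect. Sections 3.1 and 5.3.7 put every subject on standardized, weight-maintaining inpatient meals. Section 5.3.6 and Table 5.1.1 provide for insulin review and adjustment in every arm throughout the stay. Any drift these cause between Day -1 and Day 7 enters every within-arm change.

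Section 1.1 says the study should inform dose selection and insulin adjustment for later type 1 diabetes studies. The change in insulin dose bears directly on that aim, and it is one of the endpoints for which no difference from placebo is planned.

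**Working it through.** **Inputs.** Section 8.1: "The sample size target is approximately 14 subjects per study arm". For 7-point mean glucose: "Assuming a common standard deviation of 30 mg/dL in each treatment group, with 14 subjects per group, the half-width of the 95% confidence interval". The value stated there, for a dose compared with placebo, is 22.22 mg/dL. The protocol gives no SD for the five endpoints at issue, so the results below are in SD units. The 30 mg/dL is used only to check the protocol's own figure and to give a sense of scale.

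**1. The protocol's figure.** Half-width for a difference between two arms = 1.96 × SD × √(2/n) = 1.96 × 30 × √(2/14) = 22.22 mg/dL. It reproduces. With a t quantile on 26 df (2.056) it is 23.31 mg/dL. The figure is correct, and it belongs to the endpoint that already has a placebo difference.

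**2. What section 8.4.5.2 would report.** Within-arm half-width = t(0.975, 13 df) × SD/√n = 2.160 × SD/√14 = 0.58 SD (at 30 mg/dL: 17.32).

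**3. What the objectives need.** Half-width for the difference = t(0.975, 26 df) × SD × √(2/14) = 2.056 × 0.378 × SD = 0.78 SD (at 30 mg/dL: 23.31). The planned intervals are therefore about three quarters as wide as the relevant one (0.58/0.78 = 0.74).

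**4. Comparing two within-arm intervals by eye.** With equal SDs, two such intervals stop overlapping only when the means differ by more than 2 × 0.577 = 1.15 SD. The proper interval for the difference excludes zero from 0.78 SD. Judging by overlap is therefore too strict. Judging a dose by whether its own interval excludes zero (from 0.58 SD) ignores any shared change. Neither replaces the contrast.

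**5. Illustration only.** Suppose there is no drug effect and every arm shifts by the same amount. The documents give no size for such a shift. The chance that a within-arm 95% interval excludes zero (noncentral t, 13 df, noncentrality = shift in SD × √14) is then:

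| Shared shift | Within-arm interval excludes 0 | Interval for difference from placebo excludes 0 |
|---|---|---|
| 0.25 SD | 14% | 5% |
| 0.50 SD | 41% | 5% |
| 0.75 SD | 74% | 5% |
| 1.00 SD | 93% | 5% |

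This shows that the two intervals answer different questions. It is not an error rate for this trial.

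**6. Objectives against analysis text.**

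| Endpoint | Objective in 1.3 | Analysis in 8.4.5.2 |
|---|---|---|
| FPG | versus placebo | within-arm interval |
| SBP | versus placebo | within-arm interval |
| Total daily insulin dose (% change) | versus placebo | within-arm interval |
| CGMS ranges | versus placebo | summarized, contrast not stated |
| CGMS variability | versus placebo | assessed, contrast not stated |
| Urinary glucose, inhibition of reabsorption | no comparator | within-arm interval |

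The first three rows are an explicit mismatch, and the two CGMS rows are silent on the contrast. The last row has none.

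**The case against.** The case on the other side has five parts.

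- **The placebo arm is reported.** Placebo is one of the five groups, so its change and interval stand beside those of each dose, and a shared shift would show there. This stands. A reader might infer that the randomized control goes unused for these endpoints, and the protocol does not support that. But a subtraction by eye gives no stated interval for the difference, and step 4 shows how an informal reading can go wrong.
- **Baseline is already inpatient.** Subjects are admitted on Day -3 and baseline is Day -1, so part of any admission effect lies inside the baseline. This also stands. What remains is drift from Day -1 to Day 7, of unknown size.
- **There is no testing rule.** A reader might take step 5 to mean that an inert dose would be declared active some 41% of the time. The protocol does not support that either. It rules out p-values and formal tests, links no claim to an interval excluding zero, and gives no size for a shared shift. The 30 mg/dL comes from an endpoint that is not affected.
- **The CGMS wording is only silent.** This stands, and a statistical analysis plan could supply the contrast there. For FPG, SBP and insulin dose the protocol is not silent: it names the estimate and its scope, and section 8.4.5.1 shows that the placebo difference was written out where it was intended.
- **The endpoints are exploratory.** The primary endpoints are safety counts, and the main pharmacodynamic endpoint already has placebo differences and a dose-trend assessment. This limits the severity, but it does not reconcile the two sections.

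**Conclusion.** The concern holds as a mismatch between stated objectives and stated analysis. It is explicit for FPG, SBP and percent change in total daily insulin dose. For the CGMS ranges and CGMS variability the comparison asked for in section 1.3 is not carried into section 8.4.5.2. Objectives 5 and 7 are not affected.

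Two consequences follow at 14 subjects per arm. The planned half-width is about 0.58 SD where the comparison of interest has about 0.78 SD, assuming equal SDs and complete data. A change common to all arms could also be mistaken for a drug effect by a reader who looks at one dose's interval alone. How likely that is cannot be quantified from the protocol.

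The point should be fixed, but it does not endanger the trial. The endpoints are exploratory, no tests are planned, the placebo change is on display, and the data needed for the contrast are collected anyway.

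**What to change.** In section 8.4.5.2, add that for FPG, SBP, percent change in total daily insulin dose, the CGMS ranges and CGMS variability, the difference of each dose from placebo in mean change (or mean percent change) from baseline will be estimated with a 95% confidence interval. For SBP, state this for both Day 7 and Day 14, as objective 6 asks. Keep the within-arm estimates as descriptive, and keep the statement that no p-values are produced. Urinary glucose and inhibition of reabsorption can stay as they are, since objective 5 names no comparator.

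The cost is a sentence or two in the protocol and a few table columns. No new data, subjects or tests are needed. The new intervals will be wider than the within-arm ones (about 0.78 against 0.58 SD), because they carry the uncertainty of both arms.
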